5.3 Other variables

The following other variables are documented in this clinical trial:

- Demographics and other baseline characteristics (documented at Visit 1; age, sex, height, weight, race, ethnicity, localization of injury).
- Check of contraception (at Visit 1).
- Medical history and concomitant diseases (at Visit 1).
- Prior and concomitant medication (every visit)
- Diary review.

	Trial Substance:	BAY H6689	Study No.:	21559
	Short Title:	Acute Soft Tissue of the Lower Extremities	Sponsor:	BAYER HEALTHCARE LLC.

5.4 Derived variables

Area under the curves, calculated using the trapezoidal rule [1], will be determined for POM VAS pain scores and algometric tenderness. For quantitative variables the absolute changes from baseline (Visit 1) will also be determined.

5.5 Withdrawal/discontinuation

In rare instances, it may be necessary for a participant to permanently discontinue study intervention. If study intervention is permanently discontinued, the participant will remain in the study to be evaluated for efficacy and safety. See the SoA for data to be collected at the time of discontinuation of study intervention for any further evaluations that need to be completed.

A participant may withdraw from the study at any time at his/her own request or may be withdrawn at any time at the discretion of the investigator for safety, behavioral, or compliance reasons. This is expected to be uncommon. At the time of discontinuing from the study, if possible, an early discontinuation visit should be conducted, as shown in the SoA. See SoA for data to be collected at the time of study discontinuation and follow-up and for any further evaluations that need to be completed. The participant will be permanently discontinued both from the study intervention and from the study at that time. If the participant withdraws consent for disclosure of future information, the sponsor may retain and continue to use any data collected before such a withdrawal of consent.

A participant will be considered lost if he or she repeatedly fails to return for scheduled visits and is unable to be contacted by the study site. The following actions must be taken if a participant fails to return to the site for a required study visit:

- The site must attempt to contact the participant and reschedule the missed visit as soon as possible and counsel the participant on the importance of maintaining the assigned visit schedule and ascertain whether the participant wishes to and/or should continue in the study.
- Before a participant is deemed lost to follow up, the investigator or designee must make every effort to regain contact with the participant (where possible, 2 telephone calls and, if necessary, a certified letter to the participant's last known mailing address or local equivalent methods). These contact attempts should be documented in the participant's medical record.
- Should the participant continue to be unreachable, he/she will be considered to have withdrawn from the study.

The investigator will be responsible for informing the IRB/REB/IEC of the early termination of the study. Clinsearch will be responsible for notifying IECs, local authorities and the German Competent Authority, of the early termination.

5.6 Schedule of assessments

The following table shows the amended Assessment Schedule of the clinical trial.

Table 5-1: Schedule of Assessments – amended

Trial Procedure	Screening Phase		Treatment Phase											
	Screening	Baseline	Day 1		Day 2		Day 3		Day 4		Day 5		Day 6	
	Visit 1		Visit 1	Visit 2	Visit 3	Visit 4	Visit 5	Visit 6	Visit 7	Visit 8	Visit 9	Visit 10	Visit 11	
	Hours Post First Dose ➔		12 hrs	24 hrs	36 hrs	48 hrs	60 hrs	72 hrs	84 hrs	96 hrs	108 hrs	120 hrs		
Signed Informed Consent	X													
Inclusion/Exclusion Criteria Review	X													
Patient Demographics	X													
Medical History	X													
Prior and Concomitant / Medication History and Diary Review ^a	X			X	X	X	X	X	X	X	X	X	X	
History of drug, alcohol and tobacco use	X													
Body weight, height, and BMI	X													
Vital signs (incl. temperature) ^b	X								X				X	
Physical examination (injury assessment) ^c	X			X		X		X		X		X		
Injury Stratification (cohort)	X													
Urine pregnancy test	X ^f											X ^f		
Diary distribution/training	X													
Randomization/Kit assignment		X ^d												
IMP administration ^e			X	X	X	X	X	X	X	X	X	X	X	
Dispense rescue medication	X													
Rescue medicine accountability				X	X	X	X	X	X	X	X	X	X	
Algometry	X	X	X	X	X	X	X	X	X				X	
POM VAS	X	X	X	X	X	X	X	X	X				X	
Global Assessments					X ^g		X ^g		X ^g				X ^g	
Sensory Questions													X	
Diary and rescue medicine return													X	
End of Study (pt. discharged)													X	
Adverse events			X	X	X	X	X	X	X	X	X	X	X	

^a Diary review begins at Visit 2

^b Vital signs (blood pressure, respiratory rate, heart rate and body temperature after 5 minutes of rest in a sitting position).

^c Full physical exam and injury assessment at Visit 1, limited exam (injury assessment) at all other visits

^d Randomization to treatment occurs only for eligible patients.

^e All topical IMP treatments must be weighed on a digital scale, then applied by the unblinded study staff at the site. Patient will wear a blindfold when being treated.

^f Urine pregnancy test must be performed (for female patients) and the results must be negative (not pregnant) before dosing.

^g Assessments by the patient will be completed before first rescue medication is taken. If between visits, then the investigator will complete assessments at the next scheduled visit.

	Trial Substance:	BAY H6689	Study No.:	21559
	Short Title:	Acute Soft Tissue of the Lower Extremities	Sponsor:	BAYER HEALTHCARE LLC.

6 SAMPLE SIZE

This is a proof-of-concept study and therefore a specific statistical power calculation cannot be applied, however, assuming a comparable effect of the test gel vs. diclofenac – as suggested by pharmacological studies, reference is made to similar studies (Predel, Br J Sports Med 2004;38:318–323), in which the standardized effect sizes of Algometry AUC 0-72 and POM VAS AUC 0-72 were over 1; with 30:15 patients, a drop-out rate of 10 %, and a two-sided significance level $\alpha = 5\%$, a power $1 - \beta$ of about 80 % is reached.

7 DATA ENTRY AND VALIDATION

The data entry of all records documented in the CRFs is carried out by two independent data entry persons and result in two different data sets, which will be compared. Trial Master File will be corrected until conformity is proved. Furthermore, the data will be analyzed for completeness and several plausibility checks will be carried out (see Chapter 10).

8 COMPUTER SYSTEMS, SOFTWARE, AND VALIDATION OF PROGRAMS

8.1 Hardware

Used Hardware at CRMB is:

- Network servers:
- TERRA SERVER 6530 G3, 946 GB SSD, 16 GB RAM.
- Desktops (workstations):
6 Desktops based on AMD and Intel
- Scanners:
F-Secure Antivirus 7.0 for Windows Server
ESET NOD 32 Antivirus Version 9 is used on the desktops
- Backup method:
Continuous backup using VEEM.

On every Friday a full backup with Acronis True Image echo for Windows server is performed (system and data). For the rest of the week a differential backup is created. The backups are stored on internal (RAID 5) and external hard discs.

8.2 Software

Used Software at CRMB is:

- DMSys from Sigmasoft, Version 5.1,
- SAS Version 9.4,
- Windows Server 2019 Network servers,
- Windows 10 on Workstations,
- Microsoft Office 2019 and Adobe Professional for reports, tracking of CRFs.

The data management is performed using the validated Data Management System DMSys, Version 5.1, and the statistical analysis is performed using the validated statistical analysis program SAS, Version 9.4 under Windows 10.

	Trial Substance:	BAY H6689	Study No.:	21559
	Short Title:	Acute Soft Tissue of the Lower Extremities	Sponsor:	BAYER HEALTHCARE LLC.

8.3 Validation of programs

All SAS programs start with a header in which the following information is contained:

- Name of the program,
- author,
- date of creation,
- used analysis DATA sets.

All tables, graphics and listings contain in footer the name of the program with which they were created, and the date of creation.

All formats will be filed in a permanent format catalogue.

All SAS programs will be checked by a second SAS programmer responsible for the quality control (QC). He/she will also check all LOG files for ERROR messages and WARNINGS. ERRORS must not occur. WARNINGS must be checked as to whether they lead to wrong results. Furthermore, the SAS programmer responsible for the QC will check the tables, figures, and listing for completeness and consistency. The review will be documented on the Program Validation Form.

The biometrician responsible for evaluation will make sure that the specifications of planned analysis have been correctly converted in SAS programs.

8.4 Restitution of programs

All SAS programs used in the analysis as well as the OUTPUT (listings, tables) will be stored, and archived together with the source code of the programs at CRM Biometrics GmbH.

9 CODING

Concomitant medications will be coded by means of the Drug Dictionary (WHO-DD, June 2021). Adverse events and diseases will be coded using MedDRA (Version 24.0), respectively.

10 DATA CHECKS

Before starting the statistical analysis, plausibility checks will be performed. A detailed list of edit checks can be found in the Data Management Plan (DMP, Appendix 5).

11 QUERIES

After performing the plausibility checks and the comparisons of the two data entry databases, the errors of the data entry will be corrected. Queries/Data Clarification Forms will be generated in the case of inconsistencies or missing data in the CRF. According to the resolved queries, changes of the data will be performed in the Master file, if necessary. In the case of remaining unsolved queries, the Principal Investigator, the responsible statistician, the medical advisor and the project manager will decide how to handle these data and all decisions taken will be documented in detail.

	Trial Substance:	BAY H6689	Study No.:	21559
	Short Title:	Acute Soft Tissue of the Lower Extremities	Sponsor:	BAYER HEALTHCARE LLC.

12 BLIND REVIEW

A data blind review meeting will take place before unblinding the randomization code. Any potential factors that could lead to unblinding of the study will be considered before this review. A listing of all protocol deviations with the proposed classification into minor and major protocol deviations and a list of all data irregularities or unresolved queries and a proposal for how the data are to be handled in the analysis, if necessary, will be provided in the Blind Review Meeting. At least the responsible biometrist and the Clinical Project Manager will sign the Blind Review protocol.

13 DATABASE CLOSURE

After all queries have been replied, the master file will be corrected, if necessary, and the decisions regarding the handling of the unresolved queries will be made, and the database will be closed.

14 STATISTICAL EVALUATION

14.1 General

All statistical analyses will be performed in accordance with the ICH E9 guideline.

14.2 Analysis populations

The following analysis populations will be used for analysis of study data:

Safety population: The safety population will include all randomized patients who received at least one dose of the IMP. Safety (e.g., AEs) will be analyzed in this population.

Intent to treat (ITT)/ Full Analysis Set (FAS): All subjects who are randomized and provide at least one measure of primary efficacy parameters after the first application of IMP.

Per protocol (PP) population: The Per Protocol population will include all subjects in ITT who complete the study and do not have any major protocol violations. Any exclusion from PP Population will be determined and documented prior to the database lock. The primary efficacy analysis population will be PP population and ITT/FAS Population will be secondary. The same analysis on ITT/FAS Population will be repeated for the primary and secondary and other efficacy endpoints to assess the robustness of the results based on PP Population.

Before the study is unblinded, each actual post-baseline visit will be mapped to the target visit time to which it is chronologically closest. The numbering of the actual visits (from Visit 1 to Visit 11) will then be changed as needed to improve the correspondence of the actual visit times to the protocol-specified schedule. Final determinations will also be made and documented before the study is unblinded to address visits that are equidistant to two nominal visit times or any other irregularities.

Before the study is unblinded, the timing of the diary assessments will be reviewed, and assessments will be reclassified into time slots as appropriate to ensure that all assessments in a given comparison were made a comparable amount of time after start of treatment.

	Trial Substance:	BAY H6689	Study No.:	21559
	Short Title:	Acute Soft Tissue of the Lower Extremities	Sponsor:	BAYER HEALTHCARE LLC.

14.3 Patient disposition and characteristics

Demography and other baseline characteristics will be summarized descriptively for both the FAS and Safety population (if different), overall and by treatment group. Demography and other baseline characteristics will be summarized descriptively overall and by treatment group as well as by subgroup (sprains/strains, contusions). For quantitative data, means, medians, standard deviations and extremes will be determined. For qualitative data, absolute and relative frequencies will be calculated. Important baseline characteristics will be further summarized by sex, race and age.

14.4 Efficacy

14.4.1 Primary efficacy variable

The primary efficacy variable is:

- Tenderness (Algometry) over the initial 72 hours (Algometry AUC₀₋₇₂).

For the comparison of the test gel vs. placebo, the primary efficacy hypothesis to be tested is the equality of Algometry AUC₀₋₇₂, i. e.

$$H_0: \mu_T = \mu_P \text{ vs. } H_1: \mu_T \neq \mu_P.$$

The primary efficacy endpoint will be analyzed using analysis-of-covariance (ANCOVA) with treatment as the factor and baseline tenderness (algometry) as the covariate. Pair-wise comparisons may be made from above model.

The primary analysis population is the Per protocol population (PP).

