1 in 5 chance of receiving the placebo treatment. Treatment consists of a twice daily application (approximately 12 hours apart) of the assigned topical gel over 5 consecutive days, beginning on the evening of Day 1 and ending (last application) on the morning of Day 6 (total of 10 applications). All treatment applications will be performed by study staff at the site. After the first treatment, two visits each day for five consecutive days are required. Patients who experience a treatment failure can have the option of taking rescue medication for pain relief.

During the screening/baseline and follow-up treatment visits, tenderness will be measured by the pressure required to elicit a response. Pain on movement will also be rated by the subject using a 100 mm visual analogue scale.

Approximately 100 participants will be screened to achieve 75 randomized to study intervention for an estimated total of 30 evaluable participants per each active treatment and 15 participants in the placebo treatment.

Study Duration: 6 days

Treatment Duration: 6 days

Visit Frequency: After the first treatment, two visits each day for five consecutive days

Condition/Disease: Soft tissue injury, either a sprain/strain or contusion

Study Hypothesis: Topical naproxen gel, 10% effectively relieves tenderness to pressure in patients with acute soft tissue injuries

Health Measurement/Observation: Algometry measurements for tenderness and Visual Analog Scales for pain will occur pre and post topical treatment.

Number of Participants: Approximately 100 participants will be screened to achieve 75 randomized to study intervention for an estimated total of 30 evaluable participants per each active cohort and 15 participants in the placebo cohort.

Intervention Groups: Participants will be randomized in 2:2:1 fashion and stratified by injury type with at least 25 participants in the Sprain/Strain cohort and at least 50 participants in the Contusion cohort.

Data Monitoring/Other Committee: No

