4.1 Overall Design

This is a randomized (2:2:1/naproxen:diclofenac:placebo), stratified by injury (contusion or sprain/strain) active- and placebo-controlled (vehicle), double-blind, multi-center (3 sites), parallel study.

The study consists of a Screening/Baseline Phase and a Treatment Phase.

Subjects who present to the site between 6PM – 10PM and within 3 hours of injury will be recruited for the study. Eligible subjects will be selected immediately following screening/baseline evaluations. Following selection, subjects will enter the Treatment Phase. Subjects will be randomized into one of the three treatment groups in a 2:2:1 (active:active:placebo) allocation. Treatment consists of a twice daily application (approximately 12 hours apart) of the assigned topical gel over 5 consecutive days, beginning on the evening of Day 1 and ending (last application) on the morning of Day 6 (total of 10 applications). In order to assure adequate representation of different types of soft tissue injuries, at least 25 randomized subjects must enter the study with a lower extremity sprain/strain injury (cohort) and at least 50 randomized subjects with a lower extremity contusion injury (cohort).

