8.1.2 Baseline Visit 1 - (Day 1)

Patients will undergo baseline pain and tenderness testing to determine eligibility for randomization. All patients must score at least 50 on the 0 – 100 mm visual analog scale (VAS) for POM and have algometric measurement values on the injured site of $\leq 50\%$ of the respective value at the contralateral site in order to qualify for treatment. Additionally, the absolute tenderness sensitivity of the contralateral site must be at least 2.5 N/cm^2 . The investigator will stratify patients into 2 injury cohorts. One cohort is contusion cohort and the other is the sprain/strain cohort. The contusion cohort will enroll at least 50 patients and the sprain/strain cohort will enroll at least 25 patients.

The site will randomize Investigational Medicinal Product (IMP or treatment kit) based on computer generated randomization schedule stratified by injury type (either contusion or sprain/strain cohorts).

Patients entering the Treatment Phase are randomized in a 2:2:1 fashion into one of three blinded treatments:

- Naproxen Topical Gel, 10%, every 12 hours for 5 days
- Diclofenac Diethylamine Topical Gel, 2.32% every 12 hours for 5 days
- Placebo Topical Gel every 12 hours for 5 days

Patients will be reminded to discontinue use of all pain medications including supplements, use of topical heat or cold, and other products of topical application once the patient is deemed eligible to participate.

The investigator or designee will mark the injured lower extremity with a water-resistant pen so that the treatment area is consistently targeted through the Treatment Phase. After randomization, the ***first*** topical treatment will be applied the evening of Day 1. The topical treatment will be weighed on a digital scale, then applied by an unblinded study staff at the site who is not responsible for adverse events, global assessments, pain and tenderness measurements. Patients will wear a blindfold during treatment so that the identity of the IMP is blinded. Patients will be instructed to return approximately 12 hours to the site for their ***second*** treatment. The nominal repeat dosing times will be established for the rest of the study that conform to the dosing time established on Day 1.

Rescue medication will be dispensed. If the patient decides to take rescue medication prior to the next treatment, the patient will be instructed to complete the Global Assessments prior to taking the rescue medication.

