9.4.2 Primary Endpoint

The primary efficacy variable is:

- Tenderness (Algometry) over the initial 72 hours (Algometry AUC 0-72).

The primary efficacy endpoint will be analyzed if deemed necessary using analysis of covariance (ANCOVA) with treatment as the factor and baseline tenderness (algometry) as the covariance. Pair-wise comparisons may be made from above model.

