14.4.3 Other efficacy variables

Other efficacy variables are:

- VAS POM over the initial 12-hours (VAS AUC₀₋₁₂), 24-hours (VAS AUC₀₋₂₄), 36-hours (VAS AUC₀₋₃₆), 48-hours (VAS AUC₀₋₄₈), 60-hours (VAS AUC₀₋₆₀), 72-hours (VAS AUC₀₋₇₂), and 120 hours (VAS AUC₀₋₁₂₀);
- Change of VAS POM at hours 12, 24, 36, 48, 60, 72 and 120 from baseline (BL);
- VAS POM over the initial 72-hours (VAS AUC₀₋₇₂) in the subgroups “sprain/strain” and “contusion”.
- Change of Algometric Tenderness (N/cm²) at hours 12, 24, 36, 48, 60, 72, and 120 from baseline;
- Algometric Tenderness (N/cm²) over the initial 12-hours (N/cm² AUC₀₋₁₂), 24- hours (N/cm² AUC₀₋₂₄), 36-hours (N/cm² AUC₀₋₃₆), 48-hours (N/cm² AUC₀₋₄₈) 60-hours (N/cm² AUC₀₋₆₀) and 120 hours (N/cm² AUC₀₋₁₂₀);
- Ratio of algometry injured/contralateral sites over 72 hours and 120 hours (N/cm² Ratio AUC₀₋₇₂ and N/cm² Ratio AUC₀₋₁₂₀);

	Trial Substance:	BAY H6689	Study No.:	21559
	Short Title:	Acute Soft Tissue of the Lower Extremities	Sponsor:	BAYER HEALTHCARE LLC.

- Algometry over the initial 72-hours (N/cm^2 AUC_{0-72}) in the subgroups “sprain/strain” and “contusion”.
- Percent of subjects with no (zero) VAS POM at 120 hours;
- Global assessment of treatment efficacy at 24 hours, 48 hours, 72 hours, and 120 hours by patients using a 5-point scale (0=none, 1=poor, 2=fair, 3=good, 4=excellent);
- Global assessment of treatment efficacy at 72 hours in the subgroups “sprain/strain” and “contusion”.
- Change of VAS PAR at hours 12, 24, 36, 48, 60, 72 and 120 from baseline (BL).

Figures will show the time course of outcomes by treatment group for the key quantitative outcomes VAS POM, Change of VAS POM, Algometric Tenderness and Change of Algometric Tenderness. A Kaplan-Meier plot of zero VAS POM scores will also be performed, with the first time point with zero VAS POM and all subsequent VAS POM scores are zero. The primary outcome will also be summarized by center (if there is evidence of a treatment-by-center interaction), sex, age and race but without formal statistical comparisons of treatments.

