For quantitative outcomes assessed each null hypothesis will be tested with an analysis-on-covariance (ANCOVA) model including treatment group and center as main effects, and the baseline value as covariate (those outcomes for which there is a baseline). The model will be fit both with and without the treatment-by-center interaction. The primary model will be the model without the interaction. If the treatment/center interaction is statistically significant ($p < 0.05$), additional ANCOVAs will be run to identify the center(s) driving the interaction and to lay out the evidence for efficacy among the centers whose results are concordant and centers driving the interaction. ANCOVA outputs will be presented in the Statistical Appendix for the primary and various secondary outcomes to allow an outside reviewer to assess the acceptability of the primary statistical model.

The treatment effects will be estimated as mean differences between the active and placebo groups and between the two active groups with 95% confidence intervals.

The percentage of subjects with no VAS POM at 120 hours will be analyzed by means of Fisher's exact test.

The ordinal outcome (global assessment of treatment efficacy)) will be analyzed by the Cochran-Mantel-Haenszel test of general association, stratified by center and also by subgroup (strain/sprain, contusion).

Statistical test results for secondary variables will only be interpreted exploratorily.

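### Injury type is a randomisation stratum but is missing from both ANCOVAs; adding it costs 1 df and may sharpen the naproxen–placebo comparison

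*SAP*

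**What the plan says.** **Design.** The overall design (Protocol 4.1) is "stratified by injury (contusion or sprain/strain) active- and placebo-controlled (vehicle"). Protocol 8.1.2 has sites allocate treatment from a "computer generated randomization schedule stratified by injury type (either contusion or sprain/strain cohorts"). The synopsis (Protocol 1.1) gives the stratum sizes: "stratified by injury type with at least 25 participants in the Sprain/Strain cohort and at least 50 participants in the Contusion cohort". The stratum is recorded for every patient at screening (Protocol 1.3).

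**Primary model.** SAP 14.4.1: "The primary efficacy endpoint will be analyzed using analysis-of-covariance (ANCOVA) with treatment as the factor and baseline tenderness (algometry) as the covariate". Protocol 9.4.2 has the same two terms: "analysis of covariance (ANCOVA) with treatment as the factor and baseline tenderness (algometry) as the covariance".

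**Model for the other quantitative outcomes.** SAP 14.4.3 uses a "model including treatment group and center as main effects, and the baseline value as covariate". Injury type is absent here too.

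**Where injury type is used.** AUC 0-72 is to be reported separately "in the subgroups “sprain/strain” and “contusion" (SAP 14.4.3). Baseline tables are split by injury type (SAP 14.3). The ordinal outcomes use the "Cochran-Mantel-Haenszel test of general association, stratified by center and also by subgroup (strain/sprain, contusion") (SAP 14.4.3; similarly 14.5 for tolerability and the sensory questions). Neither document says why the ANCOVAs leave it out.

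**The concern.** Stratifying forces injury type to be balanced across the arms, so it contributes almost nothing to the true sampling variance of the naproxen–placebo difference. A model without injury type does not know this. Any outcome variance due to injury type stays in the residual and enters the standard error. If injury type is prognostic beyond baseline algometry, the reported SE is larger than the real one, the confidence interval is too wide and the test rejects a true null less often than 5%.

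False positives are not inflated, and under random dropout the estimate is not biased. What is at stake is precision, in a trial with only 15 placebo patients and a stated power of about 80%.

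The planned subgroup results do not supply the missing adjustment. They give separate within-stratum estimates, and with 25 sprain/strain patients allocated 2:2:1, that stratum has about 5 on placebo. The CMH strata apply to different outcomes.

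**Working it through.** **1. The plan's own power figure.** Inputs (Protocol 9.2, SAP 6): 30:15 patients, 10% dropout, two-sided α = 0.05, and a standardised effect described as over 1, taken here as d = 1.
- After dropout: 30 × 0.9 = 27 and 15 × 0.9 = 13.5.
- Noncentrality = d / √(1/27 + 1/13.5) = 1 / √0.1111 = 3.00. The two-sample t-test power is 83.3%.
- Read as a sample size, the smallest whole 2:1 design reaching 80% is 26:13 (81.8%). Dividing by 0.9 gives 28.9 and 14.4, so 29:15 against the stated 30:15.

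The plan's figure is reproduced, slightly on the safe side.

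**2. Cost of the extra term.** With three arms and 10% dropout, mean residual df are 63.5 without injury type and 62.5 with it. At 27:13.5 and d = 1, noncentral-t power is 84.00% at 63.5 df and 83.98% at 62.5 df. The lost df costs about 0.02 points.

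**3. What R² means.** R² is the share of baseline-adjusted outcome variance explained by injury type. The documents give no value, so the range 0 to 30% is an assumption. With strata of 50 and 25, the variance of the injury indicator is (1/3)(2/3) = 2/9. The implied difference between injury types is therefore √R² / √(2/9): 0.47, 0.67, 0.95 and 1.16 SD at R² = 5, 10, 20 and 30%.

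**4. Expected effect on the SE.** Leaving the factor out should multiply the reported SE by about 1/√(1 − R²): 1.026, 1.054, 1.118 and 1.195 at those four values.

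**5. Simulation.** 60,000 trials per cell. Arms of 20:20:10 (contusion) and 10:10:5 (sprain/strain); each patient lost independently with probability 0.10; baseline covariate in both models; both models fitted to the same data. The baseline-adjusted variance is 1 and d is in units of that SD. Both directions of the injury effect were run and averaged.

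| R² | SE ratio, without / with | Null rejection, without | Null rejection, with | Power, without | Power, with | Change (points) |
|---|---|---|---|---|---|---|
| 0 | 0.999 | 5.06% | 5.06% | 83.0% | 82.9% | −0.2 |
| 5% | 1.026 | 4.47% | 4.98% | 83.7% | 85.0% | +1.3 |
| 10% | 1.055 | 4.00% | 5.06% | 84.2% | 86.8% | +2.6 |
| 20% | 1.122 | 3.08% | 5.01% | 85.3% | 90.4% | +5.1 |
| 30% | 1.202 | 2.20% | 5.00% | 86.5% | 93.6% | +7.2 |

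The changes are computed from unrounded power. Their Monte Carlo SE is 0.04 to 0.11 points. The mean estimate was 0.998 to 1.002 in both models, so bias is negligible.

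**6. Cross-checks.**
- The simulated SE ratios match step 4.
- At R² = 20%, the unadjusted SE is 1.10 times its true sampling SD. The effective critical value is then 1.998 × 1.10 = 2.198, whose two-sided tail on 63.5 df is 3.2%, against 3.1% simulated.
- A separate simulation of 20,000 trials per setting, with permuted blocks of 5 within strata, gave power without and with the factor of 83.8 and 85.2% (R² 5%), 84.4 and 87.0% (10%), 85.3 and 90.2% (20%), and 86.0 and 93.5% (30%).

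**The case against.** **The gain rests on an R² that the documents do not give.** This is true. R² counts only what injury type explains beyond baseline algometry, and the entry criteria (injured side at most 50% of the contralateral value, pain on movement at least 50 mm, lesion 25 to 150 cm², injury within 3 hours) narrow the population. At R² of 1 to 2% the gain is only about 0.2 to 0.6 points. An R² of 20% needs the two injury types to differ by 0.95 SD, nearly as much as the assumed treatment effect. The 5- to 7-point gains are therefore the top of an assumed range. The asymmetry remains: close to nothing is lost at R² = 0.

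**Nothing is invalid and no target is missed.** This also stands. Power without the factor is 83% or more in every cell, and this is a proof-of-concept trial without multiplicity control. The point concerns efficiency and an analysis that does not match the design.

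**The primary model is written in the protocol, so the change may not be purely a SAP matter.** Protocol 9.4 leaves technical detail to the SAP, but 9.4.2 does name the model. The departure must be recorded, and whether it also needs an amendment is for the sponsor to assess.

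**SAP 14.4.3 can be read as putting center in the primary model.** Its wording is loose, but 14.4.1 states the primary model without center. Saying which section governs is a clarification, and the case for injury type does not depend on it.

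**Conclusion.** The point holds. Injury type is a randomisation stratum, both ANCOVAs omit it, and nothing else in the plan adjusts the overall naproxen–placebo contrast for it. The present test is valid but conservative whenever injury type is prognostic beyond baseline. Adding the factor changes power by between about −0.2 points (R² = 0) and +7.2 points (R² = 30%), and brings the error rate back to about 5%.

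These figures assume d = 1, strata of exactly 50 and 25, and random 10% dropout. The primary population is per protocol, and exclusions after randomisation can undo the balance. As an illustration, suppose two sprain/strain patients drop out of placebo. The placebo share moves from 5/15 to 3/13, or 10.3 percentage points. At R² = 20% this shifts the unadjusted contrast in that trial by about 0.103 × 0.95 = 0.10 SD. Adjustment removes that shift, which is a further reason to include the term.

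**What to change.** Before unblinding:

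1. In SAP 14.4.1, state the primary model as Algometry AUC 0-72 on treatment, injury type (contusion or sprain/strain) and baseline algometry. Report the naproxen–placebo LS-mean difference with its 95% CI from that model. Fit injury type as a main effect only; an interaction with treatment would rest on about 5 placebo patients in one stratum.
2. Add injury type to the ANCOVA in SAP 14.4.3, except for analyses within one injury subgroup.
3. Record this as a pre-specified change from Protocol 9.4.2.
4. Add one line saying that the 14.4.1 model governs the primary endpoint and that the center models in 14.4.3 and 14.6 are supportive.

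The cost is SAP wording and one degree of freedom, with no new data and no extra patients. There is time: SAP section 1 says the SAP is finalised only after the blind review meeting, so it can be changed then, provided it is fixed before the code is broken.
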